Efficacy and Safety of Dapagliflozin in Acute Heart Failure

DICTATE-AHF

NCT 04298229

Statistical Analysis Plan

Version	Approval	Summary of Changes
Number/Amendment	Date	
1.0/ Original protocol	10.2021	Not applicable
2.0/Amendment One	3.2023	 Modified text to include patients without diabetes Sensitivity endpoint analysis - changed diuretic dose analyses to be centered on 40mg IV furosemide from 20mg Defined serum potassium values to define severity categories of hypokalemia Defined serum glucose values to define severity categories of hypoglycemia and subsequent analyses changes for these new categories Added eGFR calculation to also be done with the CKD-EPI calculation Primary Analysis: changed the covariates to only be baseline weight (removing other covariates) Exploratory Outcome: Altered analysis of 30-day readmission to include death as a competing risk Exploratory Outcome: clarified total daily insulin doses will be compared between treatment arms and prior to enrollment Exploratory Outcome: Added 24-hour and spot urine sodium measures Added Heterogenicity of Treatment Effect analyses Added changes in serum chemistries by treatment arm

Introduction

This document describes the statistical analysis plan (SAP) for a randomized, open-label, multi-center trial studying the sodium-glucose cotransporter-2 inhibitor (SGLT2), Dapagliflozin, in patients with or without Type II diabetes (T2DM) admitted with acute decompensated heart failure (ADHF).

Patients with ADHF are typically admitted to the hospital due to symptoms of congestion with loop diuretics being the primary mode of treatment; however, loop diuretics are not always sufficient in helping patients achieve adequate decongestion.^{1,2,3} In fact, congestion remains the major cause of hospital readmission for heart failure. In addition, an increasing percentage of patients admitted with ADHF also have T2DM. It has been shown that SGLT2-inhibitors, approved for anti-hyperglycemic therapies, also have diuretic and natriuretic effects.⁴ The acute diuretic effects in a population with ADHF, with or without concomitant hyperglycemia, undergoing intravenous diuresis are currently unknown. This trial hypothesizes patients randomized to receive dapagliflozin will have improved decongestion when compared to those receiving structured usual care.

Treatment arms

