 - ii. Mild: serum glucose 54-69 mg/dl
 - iii. Mod-Severe: serum glucose < 54 mg/dl
 - b. Hyperglycemia is defined as:
 - a. Not hyperglycemic: serum glucose < 200 mg/dl
 - b. Mild: serum glucose 200-300 mg/dl
 - c. Severe: serum glucose > 300 mg/dl
- d) Incidence of hypovolemic hypotension, defined as symptomatic hypotension with a sustained systolic blood pressure less than 90 mmHg lasting at least 30 minutes requiring fluid administration.
- e) Inpatient mortality

Design Considerations

Randomization

Patients will be randomized in a 1:1 ratio to receive either intervention or structured usual care. Randomization will use block randomization stratified by site with block sizes of 4.

Power and Sample Size

We anticipate dapagliflozin will increase the weight loss while decreasing the cumulative furosemide dose required to achieve euvolemia. On the basis of the historical literature, we project an increase in diuretic efficiency by 0.1kg/40mg IV furosemide in the Dapagliflozin arm to be a clinically meaningful difference. We project that our diuretic protocol will decrease variations in loop diuretic dosing, which drive large standard deviations. We project a normally distributed standard deviation within each arm to be 0.25kg/40mg. A sample size of 120 experimental subjects and 120 control subjects will have 87% power to detect a probability of 0.611 that an observation in the Dapagliflozin arm is less than an observation in the structured usual care arm using a Wilcoxon (Mann-Whitney) rank-sum test with a 0.05 two-sided significance level.

Statistical Approach

Descriptive Analysis

Initially, we will describe the study cohort pooled across all sites, both overall and grouped by treatment assignment. To characterize the study sample, demographic, clinical, and lab data will be described overall and by treatment arm. Categorical variables will be described using frequencies and proportions; continuous variables will be described using means and standard deviations as well as medians and interquartile ranges (IQR). Missingness will be recorded for each variable. To further assess the distribution of variables, graphical summaries will be displayed using graphs such as box-plots, dot-plots,

violin-plots, and/or histograms. No statistical testing will be done to compare characteristics across groups. At a minimum, the following baseline variables will be described:

- Age (years)
- Sex

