Inpatient and 30-day endpoints of interest will be summarized overall and by treatment assignment. Categorical variables will be described using frequencies and proportions; continuous variables will be described using means and standard deviations as well as medians and interquartile ranges (IQR). Missingness will be recorded for each variable. For those endpoints that are a composite of multiple endpoints, such as incidence of worsening heart failure (requiring IV inotropic therapy, new admission to an ICU, new non-invasive positive pressure ventilation with bi-level positive airway pressure, or increase in the IV diuretic protocol intensity by 2 rows after Day 1 as adjudicated by the CEC) and hospital readmission within 30 days of index hospitalization discharge (for heart failure-related reasons or diabetic reasons), frequencies will be summarized overall and for each level.

No statistical testing will be done to compare characteristics across groups.

Main Analysis

All model results (unadjusted and adjusted) will be summarized with point estimates, 95% confidence intervals (CIs), and p-values displayed in tabular form or graphically, along with appropriate model fit statistics. Missingness in adjusting covariates will be addressed using multiple imputation based on predictive mean matching.

Primary Analysis: Our main analysis will be a covariate-adjusted proportional odds (PO) regression model with our outcome being cumulative change in weight per 40mg of IV furosemide equivalents from

enrollment to the minimum of Day 5 or discharge and the main predictor being treatment assignment. Adjusting covariates will be pre-specified and include baseline weight. Baseline weight will be fit with restricted cubic splines with 3 knots to relax the linearity assumptions.

Secondary Analyses:

Appropriate model diagnostics will be run to assess model fit. If model diagnostics suggest the planned approach violates necessary assumptions, alternative methods will be pursued.

- a) Binary logistic regression will be used to assess the association of the incidence of worsening heart failure as adjudicated by the CEC with treatment assignment.

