- b) A time to event analysis is proposed to assess the association of 30-day hospital readmission for ADHF or diabetes-related reasons. Cumulative incidence of hospital readmission for heart failure or diabetes-related reasons will be graphed by treatment arm death as a competing risk. Multivariable Cox proportional hazards models stratified by enrollment site will be fit to assess the association of time to hospital readmission for reasons of interest with treatment assignment.

Exploratory Analyses:

Appropriate model diagnostics will be run to assess model fit. If model diagnostics suggest the planned approach violates necessary assumptions, alternative methods will be pursued.

- a) The association of NT-proBNP at discharge with treatment arm will be modeled using covariateadjusted PO regression, adjusting for NT-proBNP at baseline (Day 1).
- b) The association of Day 2 24-hour total urine output per the following methods in which diuretic dose is centered at 40mg and values less than 40mg are winsorized to 40mg:
 - a. 40 mg of IV furosemide equivalents will be analyzed using the Wilcoxon Rank Sum test
 - b. Doubling of the loop diuretic dose to account for the logarithmic dose-response curve will be analyzed using the Wilcoxon Rank Sum test.
- c) Urine sodium-based diuretic efficiency defined as the Day 2 24-hour total urine sodium excretion (mmol) per 40mg of IV furosemide equivalents (total loop diuretic dose over Day 2) will be analyzed using the Wilcoxon Rank Sum test.
 - a. Repeated as per doubling of the cumulative Day 2 loop diuretic dose (log2 cumulative loop diuretic dose centered at 40mg) will be analyzed using the Wilcoxon Rank Sum test.
- d) Spot urine sodium-based diuretic efficiency defined as the spot urine sodium concentration (mmol/L) on Day 2 per 40mg of IV furosemide equivalents (preceding loop diuretic dose) will be analyzed using the Wilcoxon Rank Sum test.
- e) The association of Day 2 fractional excretion of sodium (FENa)-based diuretic efficiency determined from spot urine collected 2 hours after bolus loop dose with treatment arm will be analyzed using the Wilcoxon Rank Sum test.
- f) The association of Day 2 urinary Na/K ratio with treatment arm will be analyzed using covariateadjusted PO regression, adjusting for baseline (Day 1) urinary Na/K ratio.
- g) The association of calculated Day 2 6-hour sodium output with treatment assignment will be analyzed using the Wilcoxon Rank Sum test

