All multivariable models will adjust for the same key covariates as specified for the primary outcome, as sample size permits. Appropriate model diagnostics will be run to assess model fit. If model diagnostics suggest the planned approach violates necessary assumptions, alternative methods will be pursued.

- a) The association of estimated Glomerular Filtration Rate (eGFR) at discharge, calculated using the MDRD equation, with treatment assignment will be modeled using covariate-adjusted PO regression, adjusting for baseline eGFR. The analysis will be repeated calculating eGFR using the CKD-EPI equation as well.
- b) The association of the incidence of ketoacidosis as adjudicated by the CEC with treatment assignment will be analyzed using the Pearson chi-square test.
- c) Serum glucose trends over time by treatment assignment will be graphed. Descriptive statistics of the daily raw glucose values and the glycemic status during hospitalization by treatment group will be reported and compared across treatment assignment by Wilcoxon Rank Sum tests and Pearson's chi-square tests, respectively.
- d) The association of incidence of hypovolemic hypotension, defined previously, with treatment assignment will be analyzed using the Pearson chi-square test.

e) The association of inpatient mortality with treatment assignment will be analyzed using the Pearson chi-square test and univariate logistic regression.

Sensitivity Analyses:

Our sensitivity analysis will be a covariate-adjusted proportional odds (PO) regression model with our outcome being log-transformed weight at the minimum of Day 5 or discharge and the main predictor being treatment assignment. Adjusting covariates will be as defined in the primary analysis. Appropriate model diagnostics will be run to assess model fit. If model diagnostics suggest the planned approach violates necessary assumptions, alternative methods will be pursued.

Heterogenicity of Treatment Effect:

Heterogenicity of Treatment Effect (HTE) will be assessed refitting the primary model with the covariate of interest interacted with treatment assignment. The HTE analysis will include the following variables:

- Sex (male or female)
- Baseline edema score (No-Mild/Moderate/Severe)
- Baseline NTproBNP
 - Continuous
 - Dichotomize by median NTproBNP [above/below]
- Baseline BMI-adjusted BNP: defined as a 4% increase in NT-proBNP for every 1 unit increase in baseline BMI above a BMI of 20kg/m²
 - Continuous

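### Randomisation is stratified by site, but the primary proportional odds model leaves site out; if sites differ, the test is conservative and a modest amount of power is given up

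*SAP*

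**What the plan says.** - **Allocation** (SAP, Design Considerations, Randomization): "Patients will be randomized in a 1:1 ratio to receive either intervention or structured usual care" and "Randomization will use block randomization stratified by site with block sizes of 4".
- **Primary model** (SAP, Main Analysis, Primary Analysis): a proportional odds (PO) model with treatment and baseline weight, the latter as a 3-knot restricted cubic spline. "Adjusting covariates will be pre-specified and include baseline weight". The verb could be read as leaving the list open, but the SAP version table closes it: "changed the covariates to only be baseline weight (removing other covariates".
- **Readmission** (SAP, Secondary Analyses b): "Multivariable Cox proportional hazards models stratified by enrollment site will be fit".
- **Sensitivity analysis**: "Adjusting covariates will be as defined in the primary analysis". Site is not among the heterogeneity variables either, so no planned analysis of the primary endpoint uses it.
- **Safety models**: "All multivariable models will adjust for the same key covariates as specified for the primary outcome, as sample size permits".

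Protocol section 10.0 refers to the SAP for full methods. It prefers the PO model to the Wilcoxon test partly because it can adjust for baseline covariates.

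**The concern.** Blocking within site keeps the arms nearly equal in each hospital, so differences between hospitals largely cancel out of the treatment comparison. A model without site still counts those differences as residual noise. Its standard error is then larger than the estimator's real variability, and the test rejects less often than its nominal level. The design pays for balance that the analysis does not use.

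Site differences are plausible here. The denominator of the endpoint is loop diuretic dose. Patients treated before randomisation carry on from their existing regimen (Protocol 5.3.1), titration steps are suggestions (5.3.2), and the endpoint period ends at discharge if that precedes day 5 (2.1). At stake are some power and a consistent treatment of site across models. The validity of a positive result is not in question.

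**Working it through.** **1. The plan's own figure.** Inputs from SAP, Power and Sample Size: difference 0.1, SD 0.25, 120 per arm, two-sided 0.05.

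- SE = 0.25 × √(2/120) = 0.0323, and 0.1/SE = 3.098.
- Power = Φ(3.098 − 1.960) = Φ(1.138) = 87.3% (t test 87.0%).
- Probability index = Φ(0.1/(0.25√2)) = 0.611.

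The stated 87% and 0.611 reproduce. A simulated Wilcoxon test gives 85.2%, so a PO model should start near there.

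**2. Normal theory.** Let s be the share of within-arm outcome variance that lies between sites. The documents do not give it; 0 to 20% is assumed. With balance within site and total SD fixed at 0.25:

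- model SE / true SD, site omitted = 1/√(1−s)
- size, site omitted = 2[1 − Φ(1.960/√(1−s))]
- power, site omitted = Φ(1.138/√(1−s))
- power, site included = Φ(3.098/√(1−s) − 1.960)

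| s | Size, omitted (%) | Power, omitted (%) | Power, included (%) | Gain (points) |
|---|---|---|---|---|
| 0% | 5.0 | 87.3 | 87.3 | 0 |
| 2% | 4.8 | 87.5 | 87.9 | 0.4 |
| 5% | 4.4 | 87.9 | 88.9 | 1.0 |
| 10% | 3.9 | 88.5 | 90.4 | 1.9 |
| 20% | 2.8 | 89.8 | 93.4 | 3.5 |

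**3. Simulation of the PO model itself.** 240 patients, six sites, blocks of 4 within site, 3-knot spline for baseline weight (simulated as unrelated to outcome), normal outcome, effect 0.4 SD (0.1/0.25), Wald test. The protocol says up to six sites; their sizes are assumed. Set A has 90/50/35/30/20/15 patients (10,000 runs per setting) and set B has 110/50/35/25/12/8 (16,000). Entries are percentages, without → with site.

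| s | Size, A | Size, B | Power, A | Power, B |
|---|---|---|---|---|
| 0% | 5.1 → 5.4 | 5.2 → 5.5 | 85.3 → 85.9 | 85.7 → 86.2 |
| 2% | 4.9 → 5.5 | 5.2 → 5.6 | 85.4 → 86.4 | 85.7 → 86.7 |
| 5% | 5.0 → 5.8 | 4.8 → 5.7 | 85.3 → 86.9 | 85.8 → 87.6 |
| 10% | 3.8 → 5.1 | 4.1 → 5.5 | 87.0 → 89.6 | 86.2 → 89.1 |
| 20% | 3.2 → 5.6 | 3.1 → 5.9 | 87.8 → 92.4 | 87.8 → 92.9 |

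Monte Carlo SE is about 0.2 points for size and 0.3 to 0.35 for power.

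**4. Removing the liberality of the site model.** The site model runs slightly above 5%, so part of the raw gain is not real. With its likelihood-ratio test held to a true 5% (set A sizes, separate 10,000 runs), its power minus that of the planned test is −1.1, −0.7, +1.1, +1.2 and +4.0 points at s = 0, 2, 5, 10 and 20%.

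These differences carry more error. The critical value is known to √(0.05 × 0.95/10,000) = 0.22 points of size. That is about 0.22 × φ(1.138)/(2φ(1.960)) = 0.22 × 0.209/0.117 = 0.39 points of power. Two independent powers add √(0.35² + 0.35²) = 0.49. The total is √(0.39² + 0.49²), about 0.6 points. A further run on the same site sizes (about 4,000 trials per cell) gave about 0.6, 1.0 and 3.4 points at 5, 10 and 20%, and essentially none at 0 to 2%.

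**5. Where the gain comes from.** In set A, omitting site gives a ratio of model SE to true sampling SD of 1.02, 1.05 and 1.10 at 5, 10 and 20%. Adding site does not shrink the printed log-odds SE (0.229 to 0.230–0.231). Instead the log odds ratio rises (0.68 to 0.71, 0.69 to 0.74, 0.69 to 0.79), because the odds ratio is non-collapsible.

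**6. If 0.25 is the within-site SD.** Total SD then grows with s. Set B power at 2, 5, 10 and 20% is 85.0 → 86.1, 84.1 → 85.9, 82.5 → 85.9 and 79.3 → 86.2, before any size correction.

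**7. Sparse sites for worsening heart failure.** P(at least one site has no events) = 1 − Π[1 − (1−p)^m] over the set A sizes. At assumed event rates p of 5%, 10% and 20% it is 79%, 35% and 5%.

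**The case against.** The omission costs nothing in validity, and a positive result from the planned test would if anything be understated. Only a 20% site share gives a sizeable gain, and nothing in the documents supports 20%. They point towards a smaller share: one titration grid, fixed dose conversions, a standard weighing procedure, a common diet and fluid restriction, and an expectation that the protocol will reduce dosing variation. Cutting the covariates to baseline weight was a deliberate amendment, and the resulting model is close to the unstratified Wilcoxon test used for power. The readmission Cox model is the only analysis that names site, so it could be called the exception. The site model also runs slightly above 5%.

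Most of this stands as a limit on size. The net gain at a 5 to 10% share is about 1 point, close to simulation error in any one run; it is credible because theory and separate runs agree on its direction. None of it is a reason to leave out the factor that the trial randomises by, and the SAP offers no reason of its own.

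**Conclusion.** The point holds, as one of efficiency and consistency. The primary analysis omits the randomisation stratum, which the readmission model uses. If site carries 5%, 10% or 20% of outcome variance, actual size without site is about 5%, 4% or 3%. The net power given up is about 1 point at 5 to 10% and about 4 at 20%. At 2% or less there is nothing to gain. There is no bias and no inflation of type I error, and the 87% is not made wrong.

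The sizes rest on the assumed site share and site sizes, a normal outcome, and baseline weight unrelated to outcome and site. If weight tracks site, it already absorbs part of the site effect. The change is worth making because it is cheap and makes the analysis follow the design, not because the expected gain is large.

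**What to change.** Add enrolment site to the primary PO model as a categorical factor, with very small sites pooled by a rule fixed before treatment comparisons are seen; a random site effect is an alternative. State that the odds ratio is then a within-site (conditional) effect. If site is nevertheless kept out, the SAP should say why it is used in the Cox model only, and add a site-adjusted sensitivity analysis.

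The change carries over to the sensitivity model, and to the safety PO models as sample size permits. The worsening-heart-failure model ("Binary logistic regression will be used to assess the association of the incidence of worsening heart failure") names no covariates. Plain site indicators are unsafe there because some sites may have no events; use a stratified or conditional analysis, or pooled sites.

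The cost is one covariate line, a pooling rule and a sentence on the estimand. Six sites add up to five parameters, and the heterogeneity models, which refit the primary model, gain the same terms. Simulated size with site (set A) was 5.1 to 5.8% (Wald) and 5.5 to 6.0% (likelihood ratio). Pooling small sites should limit that excess, but this was not simulated.

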10.0 Statistical Methods

The full statistical methods are detailed separately in the Statistical Analysis Plan.

The primary analysis model will be the semiparametric proportional odds (PO) ordinal logistic regression model¹⁶ for continuous outcome variables¹⁷. The PO model does not make any distributional assumption for the response variable, is robust to extreme values, and is invariant to transformations of the response variable. It is also extremely efficient when compared to linear regression if normality holds. The Wilcoxon nonparametric two-sample test is a special case of the PO model, but the PO model allows for baseline covariate adjustment. Note that we use covariate adjustment instead of change from baseline so as to not assume that (1) the baseline variable is linearly related to the response variable and (2) the slope of the baseline variable is 1.0.

For binary outcomes we will use the special case of the PO model that is the binary logistic regression model.

For safety analysis of clinical lab variables we use the most powerful and least arbitrary continuous variable analyses and include the empirical cumulative distribution function of post-randomization values of these variables. These continuous analyses will also provide estimates of incidence of such outcomes as hyper- and hypo-kalemia, but will be more sensitive than using only binary responses.

Trial	Experimental agent	Mean decrease in weight (kg) Experimental, (%)	Mean decrease in weight Control, (%)	Within group SD in Experimental Group (kg)
TRUE-AHF ⁸	Ularitide			
RELAX-AHF ¹⁸	Serelaxin	3.6	3.0	4.4
ASCEND-HF ⁹	Nesirtide			
EVEREST ¹⁹	Tolvaptan	3.3	2.7	3.3
TACTICS ²⁰	Tolvaptan	3.7	2.5	4.4
Secrets of HF ²¹	Tolvaptan	3.5	2.4	2.0
ROSE-HF ²²	Nesiritide	3.25	3.5	0.9
ROSE-HF ²²	Dopamine	3.4	3.5	0.9
MEAN		3.5	2.9	2.7

Changes in body weight from admission to discharge in previous literature

Changes in weight by IV 40mg Furosemide Equivalents (FE)

Trial	Experimental agent	Duration (days)	Daily IV loop diuretic dose in FE, mean or median (IQR)*	Median (IQR) decrease in weight (kg)/40mg IV FE	Difference associated with adverse HF outcomes
RELAX-AHF ²³	Serelaxin	5	80	0.42 (1.00, 0.14)	Below median value
DIUR-HF ¹⁴	None	3-5	137 (100, 200)	0.20 (0.281, 0.082)	Below median value
ASCEND-HF ²⁴	Nesiritide	2		0.42 (1.0, 0.05)	Below median value
PROTECT ²⁵	Rolofylline	4	80 (47, 133)	0.38 (0.8, 0.13)	Below median value
EVEREST ^{19,26}	Tolvaptan	4	80	0.30 (0.79, 0.03)	Below median value

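### The worsening heart failure analysis names treatment as its only predictor; a short pre-specified baseline adjustment with site would probably gain some power at little cost

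*SAP*

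**What the plan says.** SAP, Secondary Analyses, item a): "Binary logistic regression will be used to assess the association of the incidence of worsening heart failure". The sentence ends by relating "worsening heart failure as adjudicated by the CEC with treatment assignment". No covariate and no site term follow.

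The surrounding text bears on how to read that silence:

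- The Main Analysis preamble says "All model results (unadjusted and adjusted) will be summarized" and plans multiple imputation for missing covariates. It does not say which endpoints are adjusted, or for what.
- Primary Analysis: "Adjusting covariates will be pre-specified and include baseline weight". Weight is the only covariate named.
- Secondary Analyses, item b), on 30-day readmission: "Multivariable Cox proportional hazards models stratified by enrollment site will be fit". Its covariates are not listed.
- Safety Analyses: "All multivariable models will adjust for the same key covariates as specified for the primary outcome, as sample size permits". In the same section, inpatient mortality gets a "Pearson chi-square test and univariate logistic regression".
- Protocol 10.0 prefers the proportional odds (PO) family to the rank-sum test, "but the PO model allows for baseline covariate adjustment", and names logistic regression as that family's version for binary outcomes.
- SAP, Randomization: allocation is blocked within site. SAP, Descriptive Analysis, lists enrollment NT-proBNP, eGFR and systolic pressure.

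**The concern.** Worsening heart failure is one of two secondary endpoints and the only one of the two observed in hospital. No power is stated for it, so efficiency matters. In a logistic model, adjusting for a baseline variable that predicts the outcome raises the power of the treatment test, tightens a standardised risk difference and takes chance imbalance in that variable out of the estimate. It does not narrow the interval for the odds ratio itself, because the conditional odds ratio is a different, more extreme quantity than the crude one.

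Site is a separate matter. It is the randomisation stratum and is used in item b), but item a) does not mention it. If event rates differ between sites, an analysis that ignores site gives up some of what stratification bought.

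If adjustment is intended after all, the covariates are not fixed in advance, which leaves a choice to the analyst in an open-label trial.

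**Working it through.** **1. Reading item a).** Where the SAP adjusts a named model, it usually says for what: baseline weight (primary), NT-proBNP and urinary Na/K ratio (exploratory a and f), baseline congestion (the congestion score), eGFR (safety a). Item a) carries no such phrase. The rule to reuse the primary covariates sits under Safety Analyses. Carried over to item a), it would add only baseline weight, whose value for this outcome the documents do not show. As written, the plan therefore gives an unadjusted analysis or at best a weakly adjusted one.

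**2. The plan's own power figure.** The SAP states 87% with 120 per arm, for the primary endpoint. P(X<Y) = Φ((0.1/0.25)/√2) = 0.611, as stated. Power is 87.3% by the two-means formula, 85.7% with rank-sum efficiency 3/π, 85.4% with the exact rank-sum variance, 85.2% by simulation and 84.6% by Noether's formula. The figure is reproduced within about 2.5 points, but it says nothing about worsening heart failure.

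**3. Power for item a), under assumptions.** All event rates and prognostic strengths here are assumed. Model: logit P(event) = a + b·T + s·Z, with Z standard normal and 120 per arm. The values a and a + b are set so that the average risks equal the assumed control and dapagliflozin risks. Test: two-sided Wald at 0.05, 4,000 simulated trials per setting. The strengths s = 0.5, 1.0 and 1.5 give AUC of about 0.64, 0.75 and 0.82.

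Cross-check at 20% v 10%: pooled SE = √(2 × 0.15 × 0.85/120) = 0.0461; SE under the alternative = √((0.16 + 0.09)/120) = 0.0456; Φ((0.10 − 1.96 × 0.0461)/0.0456) = 58.4%. The simulated unadjusted power was 57.3% to 59.9%.

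Power in %, unadjusted → adjusted for Z:

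| Control v dapagliflozin | AUC ≈ 0.64 | AUC ≈ 0.75 | AUC ≈ 0.82 |
|---|---|---|---|
| 10% v 4% | 40.2 → 40.0 | 40.6 → 43.1 | 41.9 → 48.3 |
| 10% v 5% | 28.1 → 28.4 | 28.6 → 30.6 | 28.0 → 33.0 |
| 20% v 10% | 58.6 → 59.8 | 57.3 → 62.1 | 59.9 → 69.5 |
| 30% v 18% | 57.8 → 60.2 | 59.6 → 65.4 | 58.2 → 71.0 |
| 30% v 15% | 80.3 → 81.9 | 79.9 → 85.2 | 79.2 → 89.1 |
| 40% v 25% | 69.0 → 71.4 | 70.4 → 78.0 | 69.4 → 82.4 |
| Change, points | −0.2 to +2.4 | +2.0 to +7.6 | +5.0 to +13.0 |

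Monte Carlo error is about √(0.5 × 0.5/4000) = 0.8 points per figure, and less for the paired differences.

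A second simulation used likelihood-ratio tests and added two noise covariates to the score. For 25% v 12% and 30% v 16%, it gave gains of 1.5 to 3.2 points at AUC 0.66, 5.3 to 5.5 at 0.72 and 7.1 to 8.0 at 0.78.

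**4. Cost if the covariates are useless.** With s = 0, one covariate changed power by −0.8 to +0.4 points. The largest loss with five useless covariates was 42.2 − 41.0 = 1.2 points.

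**5. Type I error.** With 10,000 null trials per setting, the Wald tests rejected in 3.8% to 5.4% across all models. The second simulation rejected in 5.7% adjusted and 4.9% unadjusted. With 4,000 runs the standard error is √(0.05 × 0.95/4000) = 0.34 points, so 5.7% is about 2 standard errors above 5%, and part of its smallest gains may be test size.

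**6. Number of terms.** Treatment plus three covariates makes 4 terms. Six sites, the protocol's stated maximum, add 5, making 9. Expected events at 10% v 5% are 120 × 0.15 = 18, which is 4.5 or 2.0 per term. At 20% v 10% they are 36 (9.0 or 4.0), and at 40% v 25% they are 78 (19.5 or 8.7). The list must be short and the site term needs a rule for sparse data.

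**The case against.** The strongest reply is that a treatment-only model is inferred from silence. The Main Analysis preamble speaks of unadjusted and adjusted results, and where the SAP wants a treatment-only logistic model, for inpatient mortality, it says so outright. A reader might infer from item a) that the sponsor decided against adjustment; the documents do not say that. This part of the objection stands. It does not settle the matter, because the preamble assigns no covariate to item a). Nor is item b) a full model to copy, since it lists no covariates either.

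A reader might also infer a definite loss of power. The documents do not support one. They give no event rate, effect or prognostic strength for this endpoint, and do not show that NT-proBNP, eGFR or systolic pressure predicts it. Eligibility cuts off low eGFR, low systolic pressure and anticipated inotrope need. One component of the composite is escalation on the diuretic grid, which is driven by urine output. Both may weaken the covariates, and with weak ones the gain is close to nil.

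The unadjusted comparison is also not biased. Chance imbalance is random error that its confidence interval already covers. And adjustment is not free, because it changes the odds ratio being estimated.

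**Conclusion.** The point holds as a cheap improvement to a secondary analysis. Item a) names treatment alone, omits the stratification factor and leaves unused the baseline values that the chosen model family could take in. The unadjusted analysis is valid but probably less efficient.

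Under assumed risks from 10% v 4% to 40% v 25%, adjustment adds about 0 to 2 power points with weak covariates (AUC about 0.64) and about 2 to 8 with moderate ones (AUC about 0.75). The 5 to 13 points at AUC 0.82 need a prognostic strength that nothing in the documents supports. The simulations contain no site effect, so they do not size the gain from adding site.

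No stated figure becomes wrong, since the 87% belongs to the primary endpoint. It would also be too strong to call this the trial's only in-hospital clinical efficacy endpoint: length of stay and congestion at discharge are compared too, as exploratory endpoints.

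**What to change.** Before any unblinded analysis, amend SAP Secondary Analyses, item a), to specify:

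- a logistic model of adjudicated worsening heart failure on treatment plus a short fixed list of baseline covariates: log NT-proBNP, eGFR and systolic blood pressure;
- site as the stratification factor, with small sites pooled or a penalised site term if events are few;
- a limit on the number of terms, set from the event count pooled over both arms;
- missing covariates handled by the imputation already planned;
- the adjusted odds ratio, labelled conditional, with a standardised (marginal) risk difference and 95% CI;
- the unadjusted result as supportive.

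The cost is a paragraph of SAP text and a few lines of code. The conditional odds ratio will differ from the crude one, which is why the marginal risk difference should stand beside it. If the covariates turn out not to be prognostic, about 1 power point is lost at most.
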